4.7.4.8 Time to rescue therapy

Time to rescue therapy (days) from date of randomization will be analyzed using KM and Cox proportional hazard model and displayed graphically when appropriate (Analysis population: ITT). Median event times and two-sided 95% CI for each median will be provided when appropriate. The KM survival curves will be displayed for each treatment group along with p-value for differences (each nemolizumab regimen over placebo) based on the Log-rank test stratified by baseline IGA severity (3, 4).

The estimates of the hazard ratio (HR) comparing each nemolizumab regimen with placebo will be derived using the Cox proportional hazard model for the time to event served as a response variable and treatment group, baseline IGA severity as factors. The HRs (each nemolizumab regimen over placebo), corresponding 95% CIs, and two sided p-values for the HRs will be presented.

Time to rescue therapy will be calculated for treatment period only. Subjects who do not experience the event at any time during the treatment period will be censored at the last evaluation time (up to the end of treatment period).

4.7.4.9 Change from baseline in 5-D itch scale total score at week 2

The endpoint will be analyzed using an analysis of covariance (ANCOVA), with treatment group, baseline IGA severity (3, 4) and baseline 5-D itch scale total score as covariates in the model for ITT population. A 95% CI for the difference between each nemolizumab dose regimen and placebo in LSM means and p-value will be calculated based on contrast test statistics.

4.7.4.10 Evaluation of the prurigo nodularis lesions over time

In subjects with lesions of prurigo nodularis at baseline, the lesions are evaluated at each subsequent visit (weeks 1, 2, 4, 8, 12, 16, 20, 24, 28, 32 or ET when applicable) using a 5-point scale (2: very much improved; 1: improved; 0: no change; -1: worsened; -2: very much worsened).

Number and percentage of subjects in each of five categories will be summarized by visit for ITT population.

4.8 Safety Evaluation

All safety summaries and analyses will be based upon the SAF population as defined in Section 4.4.

4.8.1 Extent of Exposure

The extent of treatment will be summarized by treatment group as follows:

- Duration of study drug (days)
- Cumulative dose of nemolizumab (mg) received
- Relative dose (%) of nemolizumab
- Number of nemolizumab administrations
- Proportion of subjects receiving scheduled study drug administrations at each study drug administration visit by treatment group

4.8.2 Adverse Events

Analysis of severity: The severity of each AE will be summarized as assessed by the investigator (Mild, Moderate, Severe). Within the same MedDRA PT, only the most severe AE for each subject will be counted in tabulations by severity. Within a MedDRA SOC, subjects with more than one MedDRA PT will be counted only once for the most severe AE reported. AEs for which the severity is missing will be imputed to be Severe; this imputation will take place prior to determining the most severe AE within a SOC or PT for a given subject.

Analysis of causality: The relationship of each AE to the study drug and/or study procedure will be summarized as assessed by the investigator (Reasonable Possibility, No Reasonable Possibility). Within the same MedDRA PT, only the AE with the highest ranked relationship to study drug and/or study procedure for each subject will be counted in tabulations by causality. Within a MedDRA SOC, subjects with more than one MedDRA PT will be counted only once for the AE that is most related to study drug and/or study procedure. AEs for which the relationship to study drug is missing will be considered as Reasonable Possibility related. The imputation for a missing relationship will take place prior to determining the most related AE within a SOC or PT for a given subject.

High-level summary of TEAEs will be presented based on 1) all causalities, 2) study drug related, and 3) study procedure (including TCS) related. The table will include the number and percentage of subjects for the following categories:

- Number of TEAEs
- Subjects with TEAEs
- Subjects with treatment-emergent SAEs (TESAEs)
- Subjects with severe TEAEs
- TEAE with fatal outcome
- Subjects temporarily discontinued from study treatment due to TEAEs
- Subjects permanently discontinued from study treatment due to TEAEs
- Subjects discontinued from study due to TEAEs

The number and percentage of subjects reporting any TEAE will be summarized by SOC and PT.

- Summary of TEAEs by MedDRA SOC and PT based on 1) all causalities; 2) study drug related, and 3) study procedure (including TCS) related
- Summary of Severe TEAEs by MedDRA SOC and PT based on 1) all causalities; 2) study drug related, and 3) study procedure (including TCS) related
- Summary of the most common TEAEs ($\geq x\%$) by MedDRA SOC and PT based on all causalities
- Summary of TEAEs by MedDRA SOC and PT based on all causalities for subgroups as described in Section 4.7.1.6

AE summaries will be ordered in terms of decreasing frequency for SOC, and PT within SOC, in the treatment group (combined, nemolizumab 90 mg, 30 mg, 10 mg, then placebo), and then alphabetically for SOC, and PT within SOC. If deemed as appropriate, a different order may be applied.

All AEs will be provided in a by-subject listing which will include both the term reported on the eCRF (verbatim term) and the PT and SOC to which it is coded. Relative start and stop days will be included along with the actual onset and resolution dates. Pre-treatment AEs will be listed separately.

4.8.3 Deaths, Other Serious Adverse Events, and Other Significant Adverse Events

Other significant TEAEs are those TEAEs reported as leading to permanent or temporary discontinuation of study treatment, leading to discontinuation of study, AESIs, and selected AEs.

The following summaries will be produced:

- Summary of TESAEs by MedDRA SOC and PT based on 1) all causalities; 2) study drug related, and 3) study procedure (including TCS) related

- Summary of TEAEs associated with permanent discontinuation of study treatment by MedDRA SOC and PT based on 1) all causalities; 2) study drug related, and 3) study procedure (including TCS) related
- Summary of AEs associated with discontinuation of study participation by MedDRA SOC and PT based on 1) all causalities; 2) study drug related, and 3) study procedure (including TCS) related
- Summary of AESIs based on 1) all causalities; 2) study drug related
- Summary of selected AEs based on 1) all causalities; 2) study drug related.

In addition, separate listings will be provided for the following:

- Deaths and other SAEs
- Permanent discontinuations of study treatment due to AEs
- Discontinuations of study participation due to AEs
- Temporary discontinuations of study treatment due to AEs
- AESIs
- Selected AEs

4.8.4 Clinical Laboratory Evaluation

All laboratory values will be reported in SI units.

Laboratory data (absolute values and change from baseline) will be summarized descriptively by visit and treatment group.

In addition, the number and percent of subjects below, within, and above the laboratory reference ranges and the number and percentage of subjects who met criteria of PCSV (see Appendix 8) will be summarized by treatment group. Shift tables will be generated using the reference ranges.

A by-subject listing of all laboratory data will be provided by treatment group, with abnormal values flagged. Laboratory reference ranges should also be listed.

4.8.5 Vital Signs, Weight, Physical Findings and Other Observations Related to Safety

4.8.5.1 Vital Signs and Weight

All vital signs and weight data (absolute values and change from baseline) will be summarized by visit and treatment group.

In addition, the number and percent of subjects with blood pressure (systolic and diastolic), pulse rate, and weight values meeting criteria for PCSV will be summarized by treatment group.

A by-subject listing of vital signs data will be provided, with potentially clinically significant values flagged.

4.8.5.2 Peak Expiratory Flow (PEF)

For subject with medical history of asthma, PEF measurements (absolute values and change from baseline for actual PEF and %predicted PEF) will be summarized by visit and treatment group.

Number and percentage of subjects who met the following criteria will be summarized.

- With %predicted PEF less than 80%
- With $\geq 20\%$ change (decrease) from baseline in PEF

A by-subject listing of respiratory assessments/PEF will be provided.

4.8.5.3 Electrocardiogram

A by-subject listing of ECG overall interpretation will be provided.

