Efficacy endpoints:	Primary efficacy endpoint 
 - Percent change from baseline in EASI to week 24 Secondary efficacy endpoints 
 - Proportion of subjects achieving IGA success (defined as IGA 0 [clear] or 1 [almost clear]) at each visit up to week 24 - Percent change from baseline in EASI at each visit up to week 24 - Absolute and percent change from baseline in weekly average of the peak and average NRS at each visit up to week 24 - Proportion of subjects with an improvement of weekly average pruritus peak NRS ≥ 4 from baseline to week 24 - Absolute and percent change in weekly average sleep disturbance NRS from baseline to week 24 - Proportion of subjects achieving PCS success (defined as a weekly prorated rounded average PCS ≤ 1 [none-mild]) at week 24 - Proportion of subjects achieving 50%, 75% or 90% reduction from baseline in EASI score (EASI-50, EASI-75, and EASI-90) at week 24 - Absolute and percent change in SCORing Atopic Dermatitis (SCORAD) score from baseline to week 24
Safety assessment:	
 - Adverse Events (AEs) including Adverse Event of Special Interest (AESI) and selected AEs at all visits - Physical examination and vital signs at all visits - Clinical laboratory values at screening, baseline, weeks 4, 8, 12, 16, 20, 24 & 32 - Electrocardiogram (ECG) at screening, baseline, weeks 1, 12 & 24 - Respiratory assessment at all visits in all subjects, and Peak Expiratory Flow (PEF) in subjects with a medical history of asthma 
An Independent Data Monitoring Committee (IDMC) will monitor the safety data at regular intervals throughout the clinical trial.

PK, pharmacodynamics (PD) and anti-drug antibody (ADA) assessment:	
 - Blood sample collection for PK at baseline, weeks 1, 2, 4, 8, 12, 16, 20, 24, 28, 32 and unscheduled visits for safety reasons - Blood sample collection for anti-drug antibody (ADA) assessment at baseline, weeks 4, 8, 16, 24, 32 and unscheduled visits for safety reasons - Blood sample collection for PD/ biomarker analyses at baseline, weeks 4, 8, 16, 24 & 32 - Blood sample collection for analysis of thymus and activation-regulated chemokine (TARC) at baseline, weeks 1, 2, 4, 8, 12, 16, 20, 24, 28 & 32 - Stratum corneum sample collection for skin biomarker analyses: baseline & week 16

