Quality-of-life (QoL) assessment:	
 - Dermatology Life Quality Index (DLQI) at baseline, weeks 2, 12 & 24 - Hospital Anxiety and Depression Scale (HADS) at baseline, weeks 12 & 24 - Missed work/school days to be recorded at weeks 4, 8, 12, 16, 20 & 24 - EuroQoL 5-Dimension (EQ5D) at baseline and week 24

Principal statistical method:
	
Primary inference for all the efficacy analyses will be based on the intent-to-treat (ITT) population at the week 24 endpoint. The primary endpoint will be analyzed using a Mixed-effect Model for Repeated Measures (MMRM) approach, including terms of treatment group, and baseline IGA severity. Visit will be fitted as a categorical variable, with the effect of treatment group and baseline varying at each visit.
 
Continuous secondary efficacy endpoints will be analyzed in a similar manner to the analysis of the primary endpoint. All categorical efficacy endpoints will be analyzed using a stratified Cochran Mantel-Haenszel test.
 
Multiple comparison procedures-modeling (MCP-Mod) approach will be applied using a set of candidate dose-response models to test for a dose-response relationship via model-associated statistics.
 
Exposure-response modeling will also be conducted for the primary endpoint of EASI percentage change from baseline at week 24, and for percentage change in pruritus NRS at week 4.
 
Primary inference for all the safety analyses will be based on the safety population. A summary of safety endpoints (treatment-emergent adverse events [TEAE], vital signs, laboratory parameters and ECG etc.) will be presented by treatment group.
 
To impute the missing values for continuous endpoints, mixed-effect MMRM approach will be used for the primary and secondary endpoints. All missing values will be treated as a non-responder for binary endpoints. All efficacy data, except in observed case analysis, will be set to missing after rescue medication is used.

Sample size:
	
Sample size is estimated using MCP-Mod approach by selecting a set of candidate dose response shapes based on primary endpoint response (percent change in EASI). Assuming placebo response of 35%, standard deviation 45% and a maximum treatment difference of 30%, 50 subjects per arm will provide at least 90% power to detect a statistically significant dose-response for at least one model at 1-sided significance level of 0.025.

Table 1 Clinical trial schematic

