9.1.5.3 Safety analyses

All safety analyses will be based on the safety population. Summary of all safety endpoints will be presented for each treatment group.

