9.1.5.3.5 Peak Expiratory Flow (PEF)

PEF measurements (absolute values and change from baseline) will be summarized by visit and treatment group. Further details on safety analyses will be provided in the SAP.

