3.2.3.3 Respiratory Assessments

At each visit, investigator or designee will perform a respiratory physical examination and ask all subjects whether they have experienced any signs/symptoms of asthma. In addition, for subjects reporting a medical history of asthma, PEF will be performed.

Newly diagnosed asthma or worsening of asthma during the study will be reported as AESI.

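### The SAP replaces the by-group ECG summary named in the protocol synopsis with a listing, and does not declare the change

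*SAP*

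**What the plan says.** The statistical paragraph of the protocol synopsis states: "A summary of safety endpoints (treatment-emergent adverse events [TEAE], vital signs, laboratory parameters and ECG etc.) will be presented by treatment group". Protocol 9.1.5.3 (Safety analyses) repeats the commitment without naming the variables: "Summary of all safety endpoints will be presented for each treatment group".

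SAP 3.2.3.1 schedules a 12-lead ECG at screening, baseline and weeks 1, 12 and 24, and at early termination or unscheduled visits where these occur. It also says that clinically significant changes from screening are reported as adverse events.

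The SAP's analysis section for ECG, 4.8.5.3, consists of one sentence: "A by-subject listing of ECG overall interpretation will be provided".

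SAP 4.11, which records changes to the planned analysis, lists two added efficacy endpoints and one revised efficacy endpoint. It does not mention ECG.

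**The concern.** The two documents disagree on what will be reported for ECG. The protocol commits to a summary by treatment group. The SAP, which is meant to carry that commitment out, provides a listing and does not say that anything has been dropped.

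Evaluating safety is a secondary objective, and the trial is meant to support the choice of dose for later development. A by-subject listing does not show whether ECG abnormalities are more frequent on nemolizumab than on placebo, or whether they rise with dose. A reader of the study report would have to count by hand, and a by-group ECG table made after unblinding would be an unplanned analysis.

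**Working it through.** No power, alpha or effect-size figure is involved, so the check is a comparison of text plus one count of records.

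**1. Is the commitment explicit?** Yes. The synopsis names ECG beside TEAEs, vital signs and laboratory parameters. Protocol 9.1.5.3 covers ECG through its general wording.

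**2. Does the SAP meet it elsewhere?** No.
- SAP 4.8.5.3 specifies a listing and nothing else.
- SAP 4.2 says that changes in categorical data will be shown in shift tables where appropriate. That is a presentation convention. It creates no ECG table when the ECG section names only a listing.
- SAP Appendices 2 and 8 set criteria for potentially clinically significant vital signs, weight and laboratory values. No corresponding criteria exist for ECG.

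**3. How does the SAP treat comparable data?** Vital signs, weight and laboratory values fall under the same kind of reporting rule as ECG: clinically significant changes from screening become adverse events.

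| Data | Clinically significant change becomes an AE | By-group summary planned in the SAP |
|---|---|---|
| Laboratory | Yes (3.2.3.4) | Values and changes by visit, reference-range counts, counts of potentially clinically significant values, shift tables (4.8.4) |
| Vital signs and weight | Yes (3.2.3.2) | Values and changes by visit, counts of potentially clinically significant values (4.8.5.1) |
| ECG | Yes (3.2.3.1) | None; listing only (4.8.5.3) |

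For the first two rows the SAP does not treat adverse-event capture as a substitute for a summary. It gives no reason for treating ECG differently.

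**4. What still reaches a by-group table?** ECG changes judged clinically significant are reported as AEs. Those that qualify as treatment-emergent are tabulated by system organ class and preferred term (SAP 4.8.2), by treatment group under the default in SAP 4.2. What has no by-group display is any abnormality or shift that the investigator does not report as an AE.

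**5. How many records are affected?** Inputs: 200 randomized subjects, 50 per group (Protocol 5.1), and three scheduled post-baseline ECGs (weeks 1, 12 and 24). Assuming full attendance:

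- all arms: 200 × 3 = 600 post-baseline ECGs
- per arm: 50 × 3 = 150

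This is an upper bound on scheduled records that appear only in a listing. It does not measure how many findings would escape the AE tables.

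**The case against.** The strongest reply is that little is at stake.
- The only place that names an ECG summary is a parenthesis in the synopsis. The subsections of Protocol 9.1.5.3 cover exposure, adverse events, laboratory data, vital signs and PEF, but not ECG.
- ECG effects are not among the potential risks in Protocol 1.2, which also reports no clinically relevant ECG findings in the phase 2a study.
- Anything the investigator considers clinically significant becomes an AE and is tabulated.

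All of this is correct and makes the point a small one. It does not remove the commitment or explain why SAP 4.11 is silent. Relying on AE capture alone also leaves the comparison to individual judgments of clinical significance at approximately 70 sites.

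A reader might infer more than the documents support, in two ways.

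*That an ECG imbalance between arms would go unseen.* It would not if the changes were judged clinically significant, because they would reach the TEAE tables.

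*That the respiratory examination and asthma questions are a second departure.* These assessments are made in every subject, the SAP plans "A by-subject listing of respiratory assessments/PEF will be provided", and by-group summaries are confined to PEF in subjects with a history of asthma. But the protocol's only specific respiratory analysis commitment is "PEF measurements (absolute values and change from baseline) will be summarized by visit and treatment group". The SAP meets it and adds percent-predicted PEF and two threshold counts. No text promises a summary of the interview answers, and the synopsis sentence on summaries does not name them. Under Protocol 7.2.5.1.1 any new sign or symptom is an AE, with no significance threshold, and newly diagnosed or worsening asthma is an AESI; SAP 4.8.2 and 4.8.3 summarize both. A table of interview answers would be an optional addition.

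**Conclusion.** The point holds for ECG. The SAP omits a by-group summary that the protocol synopsis names and Protocol 9.1.5.3 supports in general terms, and it does not declare the omission. The loss is the planned comparison across arms and doses of ECG abnormalities and shifts below the AE reporting threshold. Up to 600 scheduled post-baseline readings (150 per arm) are affected, assuming 200 randomized subjects with full attendance. The documents give no rate of non-reported ECG abnormalities, so the number of findings involved cannot be stated.

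This is a consistency defect with a modest safety consequence. It does not mean that clinically significant ECG effects would be missed, and it does not extend to the asthma interview.

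**What to change.** In SAP 4.8.5.3, keep the listing and add one table on the safety population: number and percentage of subjects in each category of ECG overall interpretation, by treatment group, at weeks 1, 12 and 24, with the shift from baseline at each visit. Baseline follows the SAP 4.2 definition. The categories should be those recorded in the eCRF, which the documents do not list.

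If the sponsor prefers the listing alone, SAP 4.11 should say so and give the reason. That would settle the undeclared change but would not restore the comparison.

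The cost is one descriptive table from data already collected and already planned for listing. There are no extra assessments and no effect on sample size or on any inferential analysis. The change should be made before database lock, when SAP 4.11 requires changes to be final.

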4.8.6 Safety Monitoring (IDMC)

An IDMC has been set-up to monitor safety data generated in this clinical trial on an ongoing basis and will make appropriate recommendations to the sponsor. The members of IDMC do not include any sponsor representative or any investigator of the study. During the clinical trial, the IDMC will review the Suspected Unexpected Adverse drug Reactions (SUSARs) and unblinded SAEs on an ongoing basis, other SAEs and AESI on a monthly basis, and accumulating safety data approximately every 4 months. The cut-off date for the first IDMC review meeting will occur once approximately 50 subjects have completed 3 months of treatment, or approximately 4 months after the first subject has been enrolled in the study (whichever is sooner). Unscheduled meetings may occur as needed at the discretion of Sponsor or the IDMC members. The IDMC will review data blinded by treatment group, but can unblind if judged to be necessary. Details on the IDMC, including the plan of analysis for IDMC outputs, the composition of the IDMC, the procedures, roles, responsibilities and their communications are provided in the IDMC charter.

4.9 Other Analyses

4.9.1 Pharmacokinetic parameters and anti-drug antibody analyses

The PK parameters derived using non-compartmental techniques will be regarded as primary endpoints for the PK analyses (see Section 3.2.4). Primary inference for all the PK parameters will be based on the PKAP population.

Descriptive statistics (n, arithmetic mean, SD, minimum, median, maximum) by treatment group will be calculated for all derived PK endpoints. When calculating the statistics on PK parameters, if the values of more than half of the measured subjects are BLQ, the statistics will not be summarized for that measurement time point, and NC (Not Calculated) will be displayed. Geometric means and between-subject coefficients of variation (CVb) will be calculated for log_e-transformed AUC_{0-28d}, AUC_{0-12w}, AUC_{0-24w}, AUC_{0-t}, AUC_{0-inf}, C_{trough} and C_{max} where:

where: SD is the standard deviation of the \log_e -transformed data.

Following \log_e -transformation, AUC_{0-28d} , AUC_{0-12w} , AUC_{0-24w} , AUC_{0-t} , C_{trough} and C_{max} will be analyzed separately using analysis of variance (ANOVA), fitting a model with treatment group as a fixed effect. The residual variance from the model will be used to calculate point estimates and 90% CIs for the least squares means for each treatment formulation on the \log_e scale. These estimates will be back transformed to give point estimates and 90% CIs on the original scale.

The concentration at each time point will be summarized as arithmetic mean, SD, median, minimum, and maximum, number of BLQs (Below the Limit of Quantification). PK parameters using geometric means will be compared to determine when steady state conditions are achieved during the treatment period.

The potential relationship between serum concentrations of nemolizumab and change in EASI, pruritus NRS, or other indicators of disease activity will be explored using PK/Pharmacodynamics (PD) modeling, as appropriate.

The following Exposure-Response analysis will be performed:

- Percent change in EASI vs individual serum concentrations (scatter plots):
 - at Week 4
 - AUC_{0-28d}
 - C_{trough} week 4
 - at Week 12
 - AUC_{0-12w}
 - C_{trough} week 12
 - At week 24
 - AUC_{0-24w}
 - C_{trough} week 24

- Percent change in weekly average of the peak pruritus NRS vs individual serum concentrations (scatter plots):
 - at Week 4
 - AUC_{0-28d}
 - C_{trough} week 4
 - at Week 12
 - AUC_{0-12w}
 - C_{trough} week 12
 - At week 24
 - AUC_{0-24w}
 - C_{trough} week 24

- Percent change in sleep disturbance NRS vs individual serum concentrations (scatter plots):
 - at Week 4
 - AUC_{0-28d}
 - C_{trough} week 4
 - at Week 12
 - AUC_{0-12w}
 - C_{trough} week 12
 - At week 24
 - AUC_{0-24w}
 - C_{trough} week 24
- Proportion of subjects achieving IGA success (defined as IGA 0 [Clear] or 1 [Almost Clear]) vs quartile of concentrations (bar plots):
 - at Week 12
 - AUC_{0-12w}
 - C_{trough} week 12
 - At week 24
 - AUC_{0-24w}
 - C_{trough} week 24
- EASI-75 response rate vs quartile of concentrations (bar plots):
 - at Week 12
 - AUC_{0-12w}
 - C_{trough} week 12
 - At week 24
 - AUC_{0-24w}
 - C_{trough} week 24
- Incidence of TEAEs in subjects treated with nemolizumab categorized by steady state trough serum concentration in 4 quartiles.

Incidence of positive ADA results will be summarized and plotted by treatment group (absolute occurrence and percent of subjects) at each visit. Incidence of treatment-related positive ADA (subjects who will become ADA positive only after Nemolizumab administration) will also be summarized and plotted by treatment group (absolute occurrence and percent of subjects) at each visit.

An interim PK and Exposure-Response analysis will be done with the bionalytical data available at Week 24 analysis (see Section 4.7.1.5). The interim analysis will include:

- Serum pharmacokinetic parameters will be listed by cohort, subject and day, and summarized by treatment.
- Serum Nemolizumab concentrations will be plotted by treatment group (individual PK profiles, mean PK profile)

- Descriptive statistics for calculated PK parameters will include: n, arithmetic mean, SD, median, minimum and maximum values.
- Geometric mean, geometric coefficient of variation (CVb), lower quartile (Q1), and upper quartile (Q3) will be presented for AUC_{0-28d} , AUC_{0-12w} , AUC_{0-24w} , AUC_{0-t} , C_{trough} and C_{max} . PK parameters will also be summarized by weight category. Analysis of PK parameters, AUC_{0-28d} , AUC_{0-12w} , AUC_{0-24w} , AUC_{0-t} , C_{trough} and C_{max} , using an analysis of variance (ANOVA) will be presented.
- The Exposure-Response analysis described above.
- Incidence of positive ADA results on individual PK profiles (plot with 3 different identifications for the negative ADA, for the treatment-related positive ADA and for the positive ADA).

